4.4.2.4 Duration of Response

Duration of response (DoR) is determined separately on disease status using RECIST v1.1 and modified RECIST, both evaluated by the investigator

Duration of response based on RECIST v1.1 assessments:

For overall responders, DoR is defined as the time from the date of first occurrence of a confirmed response (CR or PR) to date of tumor progression or death from any cause or to censoring date:

- end of response coincides with the date of tumor progression or death (in the absence of tumor progression) used for the PFS endpoint
- for a patient without disease progression or death following a response, the censored end of response coincides with the PFS censoring date (that is latest RECIST assessment or start of subsequent cancer therapy whichever occurs first)
- DoR is computed as date of PFS event or censoring minus date of first response + 1.

DoR is not defined for overall non-responders.

Duration of response based on modified RECIST assessments:

For overall responders, DoR is defined as the time from the date of first occurrence of a confirmed response (CR or PR) to date of tumor progression following that confirmed response or death from any cause or to censoring date:

- end of response will be the date of tumor progression after that confirmed response or death (in the absence of tumor progression)
- for a patient without disease progression or death following a response, the censored end of response will be the latest RECIST assessment or start of subsequent cancer therapy whichever occurs first.

DoR is not defined for overall non-responders.

Therefore, in case of disease progression followed by a confirmed response of CR or PR (and no confirmed CR or PR before the disease progression), this confirmed response will be considered as Best overall response and the duration of response will start from this confirmed response until next disease progression or death or censoring.

Additionally, a descriptive KM curve (including estimated median) for DoR is provided based on patients with an overall response.

4.4.2.5 Disease Control

Disease control is determined separately on disease status using RECIST v1.1 and modified RECIST, both evaluated by the investigator.

Disease control rate (DCR) is defined as the sum of the CR, PR and stable disease (SD) rates.

A patient with complete response followed by complete response determined on two consecutive investigator assessments (≥ 4 weeks apart) has confirmed complete response as Best Overall Response.

Otherwise, a patient with complete response followed by partial response or partial response followed by complete response or partial response followed by partial response determined on two consecutive investigator assessments (≥ 4 weeks apart) has confirmed partial response as Best Overall Response.

Otherwise, if there exists at least an assessment of CR, PR or SD, then the patient has Stable disease as Best Overall Response.

Patients who never received treatment are considered as non-responder.

4.4.2.6 QLQ-C30 questionnaire

In this study, health-related quality of life (HRQoL) are assessed using the EORTC Quality-of-Life Questionnaire Core 30 (QLQ-C30, European Organisation for Research and Treatment of Cancer 2016, Aaronson et al 1993).

The EORTC QLQ-C30 consists of 30 questions, which are combined to produce 5 functional scales (Physical, Role, Cognitive, Emotional, Social), 3 symptom scales (Fatigue, Pain, Nausea/vomiting), 6 individual symptom items (dyspnoea, insomnia, appetite loss, constipation, diarrhoea and financial difficulties) and a global health status.

A score ranging from 0 to 100 is derived for each of the functional scales, symptom scales, symptom items and the global health status according to the EORTC QLQ-C30 Scoring Manual, 3rd Edition (Fayers et al 2001). In particular:

- higher scores on the global health status and functional scales indicate better health status/function
- higher scores on the symptoms scales and symptom items indicate greater symptom burden.

If at least half the components of a scale are present in a EORTC QLQ-C30 questionnaire, the score is calculated. Otherwise, the score is set to missing.

In addition, the change from baseline (post-baseline value minus baseline value) is calculated for each of the functional scales, symptom scales, symptom items and the global health status.

EORTC QLQ-C30 questionnaire: compliance

EORTC QLQ-C30 questionnaire compliance rate over time is calculated separately for each EORTC QLQ-C30 visit (Day 1 of first 3 study treatment cycles, then with tumor assessments) by using numbers of expected questionnaires as defined below:

- the expected number of EORTC QLQ-C30 questionnaires at a specific EORTC QLQ-C30 visit is either the
 - number of patients attending Day 1 visit of cycles 1, 2 or 3, respectively
 - number of patients attending a tumor assessment visit, respectively

Number of patients with expected questionnaires, all questions completed, at least one question completed and no question at all completed are summarized at each scheduled EORTC QLQ-C30 visit.

EORTC QLQ-C30 questionnaire: summaries by visits

Summaries by visit, including changes from baseline, are provided for the EORTC QLQ-C30 scores for

- each of the 5 functional scales
- each of the 3 symptom scales
- each of the 6 individual symptom items
- the global health status.

EORTC QLQ-C30 questionnaire will not be presented for primary analysis.

4.4.2.7 Utilities collected using the EQ-5D-5L for pharmacoconomic models

The EuroQol 5-Dimension Questionnaire (EQ-5D-5L) is a self-report health status questionnaire that consists of 6 questions used to calculate a health utility score for use in health economic analysis (Herdman et al 2011; Janssen et al 2013).

There are two components to the EuroQol EQ-5D:

- a five-item health state profile that assesses mobility, self-care, usual activities, pain/discomfort, and anxiety/depression,
- a visual analogue scale (VAS) that measures health state.

Overall scores range from 0 to 1, with low scores representing a higher level of dysfunction.

Country-specific, published utility functions would allow for creation of a single summary score for health-economic modelling. Such modelling is outside the scope of this SAP.

EQ-5D questionnaire compliance rate over time is calculated separately for each EQ-5D visit (Day 1 of first 3 study treatment cycles, then with tumor assessments) by using numbers of expected questionnaires as defined below:

- the expected number of EQ-5D questionnaires at a specific EQ-5D visit is either the
 - number of patients attending Day 1 visit of cycles 1, 2 or 3, respectively
 - number of patients attending a tumor assessment visit, respectively

Number of patients with expected questionnaires, all questions completed, at least one question completed and no question at all completed are summarized at each scheduled EQ-5D visit.

Summaries by visit, including changes from baseline, are provided for the EQ-D scores for

- each of the 5 dimensions
- the visual analogue scale

EQ-5D questionnaire will not be presented for primary analysis.

4.4.3 Exploratory Efficacy Endpoints

Not applicable for this study.

4.4.4 Sensitivity Analyses

No formal sensitivity analyses are pre-planned.

4.4.5 Subgroup Analyses

Secondary efficacy endpoints are also analyzed by the following subgroups:

- ECOG Performance status: 0–1 vs. 2
- Presence of CNS metastases at baseline: yes vs. no

- Renal impairment at study entry: yes vs. no
- Creatine clearance at study entry (mL/min): 15-<30 vs 30-<60 vs >=60
- Sex: female vs. male
- HIV status: negative vs. positive
- Patients aged ≥ 65 years: yes vs. no
- Patients aged ≥ 70 years: yes vs. no
- Patients aged ≥ 75 years: yes vs. no
- Patients aged ≥ 80 years: yes vs. no
- Patients aged 65-<75 vs 75-<80 vs ≥ 80
- History of autoimmune disease: yes vs. no
- Progression on, or within 12 months of, prior platinum-based treatment: yes vs. no
- Concomitant steroid treatment ongoing at baseline: yes vs. no
- History of non-urothelial or mixed urinary tract carcinoma histology: yes vs. no
- Tumor location: Ureter vs Renal Pelvis vs all UTUC (Ureter or Renal Pelvis) vs Bladder
- Prior Lines of Treatment for Metastatic Disease (0 vs 1 vs. 2 vs. 3)
- Age-adjusted Charlson comorbidity index (AACI): ≤ 11 vs. > 11
- PD-L1 expression: IC2/3 vs. IC0/1
- PD-L1 expression by IHC Class: IC0 to IC3
- IMvigor211-like patients: yes vs. no
- Region: Australia/Canada/Western Europe vs Eastern Europe vs Other regions

All subgroup analyses are based on the same methods for statistical analyses of the respective secondary efficacy endpoint. Graphical displays such as forest plots are used to visualize the homo-/heterogeneity of secondary efficacy endpoint results across different levels of the subgroups defined above (proportions and 95% CI, or KM medians and corresponding 95% CI as applicable).

The subgroup PD-L1 expression will be derived from the percentage of tumor area infiltrating immune cells as follows:

IC=0 (<1%), IC=1 ($\geq 1\%$ - <5%), IC=2 ($\geq 5\%$ - <10%), IC=3 ($\geq 10\%$).

The subgroup “IMvigor211-like patients” is defined as follows:

Patients with:

- ECOG Performance status: 0–1
- Presence of CNS metastases at baseline: no
- Renal impairment at study entry: no
- Patient with renal dialysis reported at baseline: no
- HIV status: negative
- History of autoimmune disease: no

- Progression on, or within 12 months of, prior platinum-based treatment: yes
- Concomitant steroid treatment ongoing at baseline: no
- History of non-urothelial or mixed urinary tract carcinoma histology: no
- Prior Lines of Treatment for Metastatic Disease: 0 or 1 or 2
- Patients aged ≥ 65 years: indifferent
- Patients aged ≥ 70 years: indifferent
- Patients aged ≥ 75 years: indifferent
- Patients aged ≥ 80 years: indifferent
- Age-adjusted Charlson comorbidity index (AACI): indifferent
- PD-L1 expression: indifferent
- Region: indifferent
- Sex: indifferent

All adverse events/deaths tables and RECIST based efficacy tables by subgroup PD-L1 Expression IC2/3 vs IC0/1 will be further broken down by IMvigor211-like patients subgroup.

All RECIST based efficacy tables by subgroup PD-L1 Expression IC0/1 will be further broken down by IMvigor211-like patients subgroup and by Prior Lines of Treatment for Metastatic Disease= 0.

All RECIST based efficacy tables by subgroup PD-L1 Expression by IHC Class (IC0 to IC3) will be further broken down by IMvigor211-like patients subgroup.

All adverse events/deaths tables and RECIST based efficacy tables by subgroup PD-L1 Expression IC2/3 vs IC0/1 will be further broken down by Prior Lines of Treatment for Metastatic Disease: 0 to 3 subgroup.

All RECIST based efficacy tables by subgroup ECOG will be further broken down by the following subgroups:

- Patients aged ≥ 65 years: yes
- Patients aged ≥ 70 years: yes
- Patients aged ≥ 75 years: yes
- Patients aged ≥ 80 years: yes

Positive and negative associations between subgroups will also be tested pairwise and reported. An association between 2 subgroups is positive when lower limit of 80 % Clopper-Pearson Confidence interval of percentage of patients in subgroup 1 within subgroup 2 is higher than the percentage of patients in subgroup 1 in the whole population. An association between 2 subgroups is negative when upper limit of 80 % Clopper-Pearson Confidence interval of percentage of patients in subgroup 1 within subgroup 2 is lower than the percentage of patients in subgroup 1 in the whole population.

Associations will be tested pairwise among the following 12 subgroups: ECOG Performance status =2, Progression on, or within 12 months of, prior platinum-based

treatment, Concomitant steroid treatment ongoing at baseline, History of non-urothelial or mixed urinary tract carcinoma histology, AACI: > 11, Renal impairment at study entry, female patients, male patients, HIV status positive, History of autoimmune disease, Presence of CNS metastases at baseline, Patients aged \geq 65 years, Patients aged \geq 70 years; Patients aged \geq 75 years, Patients aged \geq 80 years and PD-L1 expression IC2/3.

Only positive and negative associations will be reported in table.

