Given the high unmet need for new therapies for advanced bladder cancer, it is of considerable interest to evaluate atezolizumab in a population of bladder cancer patients that mimics more closely a standard clinical population. As a first step in this process, the primary objective of Study MO29983 will be to analyze the safety of atezolizumab in a population of bladder cancer patients that includes patients who would have been screened out of many of the previous studies. The large majority of eligibility criteria in Study MO29983 remain unchanged from earlier trials and the safety of participants remains the highest priority. However, a small number of criteria have been broadened:

- Patients with a baseline ECOG performance status of 2 will now be eligible for enrollment, in addition to patients with ECOG performance statuses of 0 and 1
- CNS metastases will be allowed at baseline, if stable
- Patients with a renal clearance of  $\geq 15$  mL/min (rather than  $\geq 30$  mL/min) and/or a history of renal failure will be allowed in the study
- Prior treatment with non-platinum regimens will be allowed
- Patients with CNS metastases will be allowed to receive steroid treatments if the dose of prednisone is  $\leq 20$  mg/day (or equivalent)
- Patients with underlying controlled and stable autoimmune diseases will be allowed
- Patients with non-urothelial carcinoma of the urinary tract will be permitted to enroll in the trial

- Patients with HIV will be eligible, based on evidence suggesting that the PD-L1/PD-1 pathway may be operative in HIV infection and that PD-L1/PD-1 inhibition may have a role in reducing viral load

In addition to assessing safety, the current study will have secondary objectives to assess response and patient-reported outcomes, which will further advance the understanding of atezolizumab therapy in patients with cancer of the urinary tract. Finally, in exploratory analyses, the study will assess PD-L1 prevalence in tumor tissue using an IHC assay and will correlate a panel of biomarkers with efficacy and safety outcomes. These studies will continue to expand our understanding of atezolizumab and lay the groundwork for future clinical trials.

For additional rationale statements explaining the current study design, please refer to Section 3.3.

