## 6.6 SUBGROUP ANALYSES

Key safety and/or efficacy parameters will also be analyzed by the following subgroups:

- ECOG Performance status: 0–1 vs. 2
- Presence of CNS metastases at baseline: yes vs. no
- Renal impairment at study entry: yes vs. no
- Patient requiring dialysis: yes vs. no
- HIV status: negative vs. positive
- History of autoimmune disease: yes vs. no
- Progression on, or within 12 months of, prior platinum-based treatment: yes vs. no
- Concomitant steroid treatment ongoing at baseline: yes vs. no
- History of non-urothelial urinary tract carcinoma histology: yes vs. no
- Previous lines of cancer therapy (1 vs. 2 vs. 3)
- Age-adjusted Charlson comorbidity index (AACI):  $\leq 11$  vs.  $> 11$
- PD-L1 expression: low vs. high (cut-offs to be defined)
- Region (grouping countries into regions will be specified in the Statistical Analysis Plan)

All subgroup analyses will be based on the same methods as overall analyses of the primary and secondary variables. In addition, graphical displays such as forest plots will be used to descriptively visualize the homogeneity of key safety and efficacy parameters (proportions and 95% CI, or KM medians and corresponding 95% CI, as applicable will be displayed) across different levels of the pre-specified subgroup variables.

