- Number of death events, overall and by primary cause of deaths, occurrence of an autopsy, number of death events within 30 days/ later than 30 days to 90 days and later than 90 days after first study treatment administration, number of death events within 30 days/ later than 30 days to 90 days and later than 90 days after last study treatment administration
- Number of death events by number of cycles started (1 cycle, 2 cycles, 3 cycles, 4 cycles, 5 cycles or more and broken down by number of days since last dose: ≤ 30 days, $>30 - \leq 90$ days or >90 days) and by primary cause of death and occurrence of an autopsy. A death event will be associated with the number of cycles the patient received, a cycle being counted when dose >0 . A summary table and the corresponding figure will be provided.

By-patient listings based on the safety population will be provided for the following types of AEs:

- TEAEs and AEs who do not meet the criteria of TEAEs
- AEs of special interest
- AEs leading to permanent treatment discontinuation
- SAEs
- Fatal AEs (i.e. grade 5 AEs)

In addition, a by-patient listing of death case will be provided based on the Safety Population. Deaths events will be categorized in days since first dose and days since last dose: ≤ 30 days, $>30 - \leq 90$ days or >90 days in this listing.

In the above listings, information relative to the following subgroups of interest will be included:

- ECOG Performance status: 0–1 vs. 2 (the category 2 includes patients who recorded status 2 at screening but 3 at baseline)

- Progression on, or within 12 months of, prior platinum-based treatment: yes vs. no
- Concomitant steroid treatment ongoing at baseline: yes vs. no
- History: non-urothelial or mixed urinary tract carcinoma histology vs urothelial
- AACI: ≤ 11 vs. > 11
- Renal impairment at study entry: yes vs. no
- Sex: female vs. male
- HIV status: negative vs. positive
- History of autoimmune disease: yes vs. no
- Presence of CNS metastases at baseline: yes vs. no
- Patients: < 65 years vs. ≥ 65 years
- Patients: < 70 years vs. ≥ 70 years
- Patients: < 75 years vs. ≥ 75 years
- Patients: < 80 years vs. ≥ 80 years
- Prior Lines of Treatment for Metastatic Disease: 0 vs 1 vs. 2 vs. 3
- PD-L1 expression: IC2/3 vs. IC0/1
- PD-L1 expression: IC0 to IC3
- IMvigor211-like patients: yes vs. no
- Regions: Australia/Canada/Western Europe vs Eastern Europe vs Other regions

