In addition, the AE summary table described previously in this section will be repeated for each of the above subgroups.

A by-patient listing of immune-related thyroid disorders on the safety population will also be provided.

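### The SAP pools non-urothelial with undefined mixed histology, so no planned efficacy or adverse-event table isolates non-urothelial patients

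*SAP*

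**What the plan says.** Protocol 1.4 lists the eligibility criteria that were broadened relative to earlier atezolizumab studies, which took urothelial carcinoma only. One of them is "Patients with non-urothelial carcinoma of the urinary tract will be permitted to enroll in the trial". The study title names urothelial and non-urothelial carcinoma together.

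Protocol 6.6 then states that "Key safety and/or efficacy parameters will also be analyzed by the following subgroups", and the list includes "History of non-urothelial urinary tract carcinoma histology: yes vs. no".

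The SAP words this subgroup differently wherever it is used for outcomes:

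- Efficacy subgroups (SAP 4.4.5): "History of non-urothelial or mixed urinary tract carcinoma histology: yes vs. no".
- Adverse-event listings (SAP 4.6.2): "History: non-urothelial or mixed urinary tract carcinoma histology vs urothelial". The same section adds that "the AE summary table described previously in this section will be repeated for each of the above subgroups".
- The IMvigor211-like definition (SAP 4.4.5) requires "History of non-urothelial or mixed urinary tract carcinoma histology: no".
- The pairwise association analysis (SAP 4.4.5) uses the same pooled category.

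SAP 4.3 plans baseline frequency tables of histological type and of the non-urothelial, squamous, glandular and neuroendocrine sub-types, together with by-patient baseline listings. SAP 4.4.4 plans no sensitivity analyses.

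**The concern.** A tumour of mixed histology would ordinarily be understood to have a urothelial component. Pooling such tumours with squamous, glandular and neuroendocrine carcinoma gives a level whose result may resemble neither part. A reader who wants response, survival or adverse-event rates for non-urothelial carcinoma will look at this row, and it does not answer that question.

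This subgroup matters more than most. Protocol 1.2 says the prognosis of most advanced non-urothelial forms is poor and that few trials have addressed them. Results in this group are part of what the trial could add to the earlier urothelial-only studies.

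No error rate is at stake, since SAP 2.3 states that there is no formal hypothesis and that all analyses are descriptive. What is at stake is whether the subgroup row can be interpreted and traced back to the protocol.

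**Working it through.** **1. The plan's own figure.** The only sample-size figure in the documents is the precision statement in SAP 2.3 and Protocol 6.1. Exact Clopper-Pearson limits for 5/1000 are 0.16% and 1.16%, and the half-width is (1.16 − 0.16)/2 = 0.50%. This and the other eight rows of the table reproduce. The present point does not depend on it.

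**2. The definitions side by side.**

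| Place | Category used | Outcome reported on it? |
|---|---|---|
| Protocol 6.6 | non-urothelial, yes/no | yes, safety and/or efficacy |
| SAP 4.4.5 efficacy subgroups | non-urothelial or mixed, yes/no | yes |
| SAP 4.4.5 IMvigor211-like | excludes non-urothelial and mixed together | yes |
| SAP 4.4.5 associations | non-urothelial or mixed | no, baseline associations only |
| SAP 4.6.2 listings and repeated AE summary | non-urothelial or mixed, against urothelial | yes |
| SAP 4.3 baseline tables and listings | histological type and sub-types | no, baseline only |

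Protocol Appendix 8, to which inclusion criterion 4 points, lists squamous, glandular and neuroendocrine tumours and adds a note on Bellini collecting duct tumours. It has no mixed urothelial category. Neither document defines mixed histology. Every SAP outcome table split by histology uses the pooled level.

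**3. What pooling could hide.** Let m be the share of mixed patients in the pooled level, p the response rate in non-urothelial patients and q the rate in mixed patients. Then

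pooled rate = (1 − m) × p + m × q.

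The documents give none of m, p or q, so all three are assumed here.

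| m | p = 5%, q = 15% | p = 10%, q = 15% | p = q = 15% |
|---|---|---|---|
| 25% | 0.75 × 5 + 0.25 × 15 = 7.5% | 11.25% | 15% |
| 50% | 0.50 × 5 + 0.50 × 15 = 10.0% | 12.5% | 15% |
| 75% | 0.25 × 5 + 0.75 × 15 = 12.5% | 13.75% | 15% |

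In the first column the pooled row exceeds the non-urothelial rate by 2.5, 5.0 or 7.5 percentage points. In the last column the difference is zero. With the rates reversed (p = 15%, q = 5%, m = 50%) the pooled rate is again 10.0%, now 5 points too low.

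**4. How precise a separate row would be.** Exact 95% intervals for an observed 10% response rate:

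- 2/20: 1.2% to 31.7%
- 3/30: 2.1% to 26.5%
- 5/50: 3.3% to 21.8%

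As a rough guide to size, Protocol 1.2 puts squamous tumours at 1–2%, adenocarcinoma at 1% and small cell carcinoma below 1% of bladder cancers. If enrolment mirrored these shares (an assumption), the three types would total between 1 + 1 + 0 = 2% and 2 + 1 + 1 = 4%, or about 20 to 40 of 1000 patients.

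**The case against.** The strongest reply is that the SAP may only be spelling out what the protocol meant. A yes/no split has to put mixed tumours somewhere, and the protocol does not say where. A history of non-urothelial histology can reasonably be read to include a tumour with a non-urothelial component. A reader might infer from the two wordings that the SAP has replaced a protocol subgroup with a wider one. The documents do not establish that. What stands is that mixed is undefined, its relation to Protocol 6.6 is unstated, and on either reading the non-urothelial patients are not shown separately.

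The pooling also has a logic. It leaves a purely urothelial reference group, and it collects patients outside the earlier urothelial-only studies, which suits the IMvigor211-like definition. The SAP does not give this reason. It is a good argument for keeping the pooled row, but not for having no other.

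A third reply is that a separate row would be too imprecise to use. The 5/50 interval does cover both 5% and 15%, so the row could not reliably tell those rates apart. But SAP 4.4.5 already keeps levels that may be small, such as HIV-positive patients, CNS metastases and creatinine clearance of 15 to under 30 mL/min. It also already shows pooled rows beside their components: ureter and renal pelvis beside all upper-tract tumours, and the individual PD-L1 classes beside the two-level split.

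Finally, a non-urothelial row would itself pool tumours with different natural histories. That is true, and it limits what the row can say. It would still correspond to the population named in the title.

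**Conclusion.** The point holds as one of interpretability and traceability. No planned efficacy or adverse-event table isolates non-urothelial patients, and the SAP neither defines mixed nor explains the change of wording.

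Two further inferences go too far. A reader might conclude that the trial cannot report on non-urothelial carcinoma. It can: histological type and sub-type are collected and listed, so a split is possible, but it would be post hoc. A reader might also conclude that the pooled row overstates response in non-urothelial patients by a known amount. Any such figure only restates the assumed rates and mix. The distortion ranges from zero at equal rates to 7.5 points in the cases tabulated, and its direction depends on which group responds better.

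The primary endpoint, the main estimates and the sample-size table are unaffected. This is a low-cost improvement worth making, because it lets the trial report on a population that it newly admitted.

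**What to change.** - In SAP 4.4.5, and in the adverse-event summary by subgroup in SAP 4.6.2, report three histology levels: urothelial only, mixed, and non-urothelial only. Keep the pooled row as an extra, as is already done for upper-tract tumours and PD-L1.
- Define mixed in terms of the histology fields collected for SAP 4.3.
- State in one sentence how the SAP categories relate to the subgroup in Protocol 6.6.
- Leave the IMvigor211-like definition unchanged.

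The cost is SAP wording and added levels in existing tables, with no new data collection. The drawback is small cells with wide intervals, so the new rows should be presented with exact intervals and read as descriptive.
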